Cardiovascular disease (CVD) is the leading cause of death in Veterans with type 2 diabetes (T2D). Lifestyle modifications, including increased physical activity, are recommended as first-line therapy for the management of T2D. Unfortunately, the efficacy of these lifestyle interventions for preventing CVD morbidity and mortality in patients with T2D is not well-established. Available evidence from our group and others indicates that vascular adaptations to exercise training are impaired in subjects with T2D. We propose that diminished vascular adaptations explain why increased physical activity does not lead to a robust reduction in CVD morbidity and mortality in T2D. However, the mechanisms responsible for this deficit in vascular adaptations to exercise in T2D remain unknown. This is a major limitation for identifying new adjuvant therapeutics to maximize the cardiovascular benefits of exercise in the diabetic population. Exercise exerts direct effects on the vasculature via repetitive exposure to hemodynamic stimuli or shear stress. The increased blood flow and luminal shear stress attendant to each bout of exercise are primary mechanisms contributing to vascular adaptations. Shear stress is detected by mechanosensitive endothelial luminal structures, such as the glycocalyx, that convert mechanical forces into biochemical signals via mechanotransduction. As such, we propose that an intact endothelial glycocalyx is required for the mechanotransduction of increased shear stress and the subsequent chronic vascular adaptations associated with exercise to occur. Notably, glycocalyx degradation is a classic feature of T2D. Accordingly, our overarching hypothesis is that endothelial glycocalyx degradation is a key factor precluding shear stress mechanotransduction and consequent exercise-induced vascular adaptations in T2D. The corollary to this hypothesis is that restoration of the endothelial glycocalyx by dietary supplementation of glycocalyx precursors (DSGP) will improve vascular adaptations to exercise in T2D. Specifically, in Aim 1 (*Proof of Concept Clinical Trial Phase*), we will document that DSGP enhances endothelial glycocalyx integrity in patients with T2D. Although we provide preliminary evidence that DSGP can increase glycocalyx thickness and endothelial function in a mouse model of T2D, this will be the first study to demonstrate these effects in T2D subjects. The effects of DSGP for eight weeks will be studied using a double-blinded randomized placebo control trial. Subsequently, in Aim 2 (*Expanded Clinical Trial Phase*), we will demonstrate the permissive role of the endothelial glycocalyx in exercise-induced vascular adaptations in patients with T2D. Having shown that restoration of the endothelial glycocalyx via DSGP is feasible in T2D subjects, we will now investigate whether such supplementation will potentiate exercise training-induced improvements in endothelial function. This will be accomplished in a factorial balanced design in which T2D subjects will be randomized to DSGP or placebo with and without concurrent exercise training for eight weeks. Our team is poised to move cardiovascular and diabetes research forward with a translational project that will exert a sustained, powerful impact across a number of levels of inquiry that are novel conceptually, methodologically, and therapeutically. Indeed, targeting the glycocalyx holds extraordinary promise for achieving optimal exercise-induced vascular adaptations in Veterans with T2D, thus maximizing the cardiovascular benefits of exercise.

2.0 Introduction

The prevalence of type 2 diabetes (T2D) continues to increase in the US, with 26.8 million adults carrying a diagnosis.¹⁻³ Importantly, T2D is widespread among our Veterans, and the VA administration spends \$1.5 billion annually in diabetes care.^{4,5} This T2D epidemic also contributes to the staggering rates of cardiovascular disease (CVD) and cardiovascular mortality.⁶ Indeed, eight out of 10 patients with T2D die from CVD.⁷ Mechanistically, endothelial dysfunction, defined as a pathological state typified by oxidative stress, inflammation, reduced nitric oxide bioavailability and impaired endothelium-dependent vasodilation, is the most prevalent vascular characteristic implicated in the increased incidence of CVD in T2D.⁸⁻¹¹

Current standards of medical care for T2D emphasize prioritizing the use of therapies that decrease CVD risk.¹² Lifestyle modifications, such as increased physical activity, are recommended as first-line therapy for the management of T2D.¹² Unfortunately, as shown in the LookAhead trial, the efficacy of these interventions for preventing CVD morbidity and mortality in patients with T2D remains questionable.¹³ Evidence from our laboratory and those of others indicate that exercise training in T2D subjects does not elicit optimal vascular adaptations, including improvements in endothelial function.¹⁴⁻¹⁷ In fact, a recent meta-analysis concluded that exercise-induced “*improvements in endothelial function in T2D patients are weakened compared with non-diabetics*”.¹⁵ This represents an important scientific premise of this project. Restricted vascular adaptations to exercise training in T2D individuals may also contribute to their poor gains in cardiorespiratory fitness.¹⁸ Importantly, it is likely that such lessened vascular adaptations explain why increased physical activity does not lead to a robust reduction in CVD morbidity and mortality in T2D. A better understanding of the mechanisms responsible for the deficit of vascular adaptations to exercise in T2D is required for identifying new adjuvant therapeutics aimed at maximizing the cardiovascular benefits of exercise.

In the present proposal, we put forth the **idea** that an intact endothelial glycocalyx is a requisite for exercise-induced shear stress mechanotransduction to exert favorable vascular adaptations. The effects of exercise on the vasculature extend beyond improvements of traditional cardiovascular risk factors.¹⁹⁻²² It is now well-recognized that increased blood flow and associated luminal shear stress, the tangential force caused by the friction of flowing blood on the endothelial surface, are critical exercise-induced signals that lead to enhanced endothelial function,^{19, 23-27} another important premise of this project. This concept is supported by results from cell culture and isolated vessels,²⁸⁻³² as well as by *in vivo* animal^{33, 34} and human experiments.^{19, 35-41} It also implies that the endothelium is “equipped” with sensors that transduce such mechanical forces.^{42, 43} One such key mechanosensor is the glycocalyx,⁴²⁻⁴⁶ a mesh of negatively charged sialic acid-containing glycosaminoglycans and proteoglycans located on the surface of endothelial cells.^{45, 47, 48} Heparan sulfate is the most abundant glycosaminoglycan in the endothelial glycocalyx, followed by chondroitin sulfate and hyaluronic acid. The main proteoglycans are syndecan-1, -2, -4 and glypican-1. Through its interactions with the circulating blood and plasma proteins, membrane ion channels and cortical actin, the glycocalyx operates as the major mechanosensing and mechanotransducing structure in the endothelium.^{42, 43, 49, 50} Accordingly, we posit that the endothelial glycocalyx plays a permissive role in shear stress-induced vascular adaptations and that, as such, an intact glycocalyx is vital for exercise-induced vascular adaptations to be fully realized. Unfortunately, T2D is accompanied by glycocalyx degradation, presumably rendering the endothelium unable to respond and optimally adapt to exercise-induced shear stress stimuli.

The primary goal of this project is to establish the **endothelial glycocalyx as a novel target organ for heightening exercise-induced vascular adaptations**. To that end, a dietary supplement that contains glycocalyx precursors (glucosamine sulfate, fucoidan, superoxide dismutase, and high molecular weight hyaluronan) will be used as an innovative “tool” to restore the endothelial glycocalyx in T2D subjects. Demonstration that **dietary supplementation of glycocalyx precursors (DSGP)** is effective at enhancing endothelial glycocalyx integrity in patients with T2D will be accomplished in the *Proof of Concept Clinical Trial Phase* (or Aim 1) of this project. Subsequently, in the *Expanded Clinical Trial Phase* (or Aim 2), the use of the DSGP will allow us to test the hypothesis that glycocalyx restoration re-sensitizes the endothelium to shear stress mechanotransduction and thus potentiates exercise-induced vascular adaptations. This project will be the first to determine if targeting the glycocalyx is a viable therapeutic strategy for boosting exercise-induced endothelial benefits in diabetes. The present protocol will only describe the experimental strategy for the *Proof of Concept Clinical Trial Phase*.

3.0 Objectives

Our overarching hypothesis is that endothelial glycocalyx degradation is a key factor that precludes shear stress mechanotransduction and consequent exercise-induced vascular adaptations in T2D. (Figure 1). A corollary to this hypothesis is that restoration of the endothelial glycocalyx by DSGP will improve vascular adaptations to exercise in T2D.

Specific aims are as follows:

Aim 1 (Proof of Concept Clinical Trial Phase): Document that DSGP enhances endothelial glycocalyx integrity in Veterans with T2D. Although we provide preliminary evidence that DSGP can increase glycocalyx thickness and endothelial function in a mouse model of T2D, this will be the first study to demonstrate these effects in T2D subjects. The effects of DSGP for eight weeks on glycocalyx integrity and endothelial function will be studied using a double-blinded randomized placebo control trial.

Aim 2 (Expanded Clinical Trial Phase): Demonstrate the permissive role of the endothelial glycocalyx for exercise-induced vascular adaptations in Veterans with T2D. Having shown that endothelial glycocalyx restoration via DSGP in T2D subjects is feasible, we will now investigate whether such supplementation potentiates exercise training-induced improvements in endothelial function. This will be accomplished with a factorial balanced design in which T2D subjects will be randomized to DSGP or placebo with and without concurrent exercise training for eight weeks.

RELEVANCE TO VETERANS AND THE VA: Targeting the glycocalyx holds extraordinary promise for achieving optimal exercise-induced vascular adaptations in T2D, thus maximizing the cardiovascular benefits of exercise.

[figure not shown]

Figure 1. Overarching hypothesis: Endothelial glycocalyx degradation (left side) is a key factor precluding shear stress mechanotransduction (i.e., it renders the endothelium unable to detect shear stress forces) that makes T2D individuals exhibit diminished exercise-induced vascular adaptations. Restoration of the glycocalyx (right side) reinstates shear stress echanotransduction, permitting optimal exercise-induced vascular adaptations.

5.0 Study Procedures (*Proof of Concept Clinical Trial Phase*)

5.1 Study Design

Aim 1 (*Proof of Concept Clinical Trial Phase*): Document that DSGP enhances endothelial glycocalyx integrity in Veterans with T2D.

Rationale. Based on our preliminary data showing that DSGP augments endothelial glycocalyx thickness and vasodilatory responses in a mouse model of T2D (**Figure 2**), the purpose of this Aim is to demonstrate that these effects are applicable to Veterans with T2D. Importantly, our results should establish for the first time that glycocalyx restoration is accompanied by improvements in endothelial function, providing support for our proposal that the glycocalyx is a key therapeutic target to combat vascular complications in diabetes. Finally, the results obtained in Aim 1 will set the stage for an expansion of the clinical trial (Aim 2) designed to elucidate if restoration of the endothelial glycocalyx enhances exercise training-induced vascular adaptations in T2D subjects.

Hypothesis. We hypothesize that DSGP will enhance endothelial glycocalyx integrity in T2D subjects and that this effect will be associated with increased shear stress mechanotransduction and endothelial function.

Study Design and Recruitment of Participants. We will employ a double-blinded randomized placebo control trial designed to determine the effects of DSGP on endothelial glycocalyx integrity and endothelial function

(**Figure 9**). Veterans diagnosed with T2D (n=24), 45- 74years of age, will be recruited from the Harry S. Truman Memorial VA Hospital in Columbia, Missouri. The selected age range aligns with data from the Centers for Disease Control, indicating that the incidence of T2D in Veterans continues to increase after even after 65 years of age.⁴ Subjects will be classified as having T2D based on physician diagnosis, following the American Diabetes Association guidelines.⁵¹

Randomization and Blinding. Participants will be assigned to DSGP or placebo using block randomization to achieve balance in the allocation of participants to treatment arms. Randomization order will be provided to the investigational pharmacy for intervention allocation. Preparation and administration of the supplement/placebo capsules will be directed by the VA Hospital Investigational Pharmacy. All members of the investigative team involved in data acquisition and analysis will be blinded to group assignment, and subjects will not be informed of their group status.

DSGP Intervention and Outcome Measures. Participants will ingest 3,712mg (*i.e.*, six capsules) of DSGP, or placebo capsules, daily for eight weeks (+/-4 days). *Capsules should be swallowed and not crushed and ingested with meals (3 capsules every 12 hours).* DSGP, commercially available as Endocalyx™ (Microvascular Health Solutions LLC, Alpine, UT), include glucosamine sulfate, fucoidan, superoxide dismutase, and high molecular weight hyaluronan. An ongoing study using DSGP in chronic kidney disease patients (NCT03889236), to our knowledge, has not reported serious adverse side effects (*see enclosed letter from [name] and [name]*). Results from our pre-clinical studies in diabetic mice treated with DSGP (100mg/kg/day) for four weeks support that the proposed dosing regimen in humans will be capable of restoring the glycocalyx, particularly when considering the dose conversion from mouse to human. The use of Endocalyx in this study is filed under the research IND 164629 that was submitted on 11/23/2022.

[figure not shown]

Figure 2. Experimental design in Aim 1. DSGP, dietary supplementation of glycocalyx

5.2 Recruitment Methods

[name], co-PI in this proposal, is the Chief of Endocrinology at the Harry S. Truman VA facility and will direct recruitment efforts. Approximately 200 participants will be enrolled (consented) to participate in this study to obtain the sample sizes of n=24 (Aim 1) and n=72 (Aim2.) Patients will be recruited from the Endocrinology Clinic as well as Primary Care Clinics at the Truman VA Hospital. During the fiscal year 2020, the Endocrinology Clinic evaluated 1476 patients diagnosed with T2D. Thus, our Endocrinology clinic has sufficient patients to serve as potential study subjects over the duration of this study. Further, we are cognizant that patients with T2D are also frequently evaluated in the primary care setting. Our primary care clinics serve 32,400 Veterans and 9,400 of those have a diagnosis of T2D (29%). To this end, we have established a collaboration with [name] (Chief of Staff and primary care physician at the VA Hospital) to facilitate recruitment efforts in these clinics.

An Informational session about the project will be held with other primary care physicians at the VA who may also be interested in partnering with recruitment efforts.

For patients identified as potentially eligible in the Diabetes Clinic, [name] or a designated study team member will approach them in person during their visit with written information (IRB approved) as well as with contact information for the patient to communicate with study coordinator in case of questions or interest in participating. For those potential participants that seem eligible based on this pre-screening review (primary care clinics), recruitment letters (IRB approved) informing them of the opportunity to participate in this research will be mailed or shared through the VA patient portal.

Advertisement fliers and postings will also be placed in MU Info and in publicly accessible areas in the community (i.e. coffee shops, grocery stores, parks, libraries, etc.) to facilitate the recruitment of benefit eligible veterans from the surrounding community.

In the unlikely event that the above recruitment strategies are not successful, we will pursue the following alternative strategies (with IRB and office of research approval):

- Posting of advertisement flyers throughout approved venues at the Harry S. Truman VA Hospital and local primary care clinics (CBOC)s
- Systematic review of charts from primary care and endocrinology clinics with previous approval from the different providers.
- Advertisement in social media outlets, local radio and TV stations.
- Submission a search request to the VA data warehouse (VINCI) for a listing of patients at the Harry S. Truman VA who have a diagnosis of T2D and are within the targeted age range and fulfil inclusion/exclusion criteria.

Screening Procedures:

Interested participants will be instructed, via letters, flyers, or via VA patient portal to contact study coordinator for a 10-minute interview (using a waiver of documentation of consent approved by the local IRB). The interview will be conducted with the goal of determining eligibility (demographics, height, weight, current medical illnesses/ medical history, and use of medications will be obtained). If a subject expresses interest to participate in the study, a screening visit will be scheduled.

Participant Compensation:

We have completed multiple clinical studies involving human subjects with adherence rates of greater than 95% and subject retention rates of greater than 85%. We utilize a validated retention strategy published by Jeffrey et al (Am J Clin Nutr. 2003;78(4):684-689) that has been successful. With respect to subject honoraria, subjects will be paid \$25 after completion of the screening visit, \$75 after the baseline visit, and \$255 after the final visit. Subjects will also receive travel compensation of \$0.41/mile

traveled (round trip) from their residence to the Harry S. Truman VA Hospital and Clinics for each of their study visits. If subjects are asked to repeat safety labs, you will be compensated for applicable travel at a rate of \$0.41/mile traveled (round trip) from their residence to the Harry S. Truman VA Hospital and Clinics. Thus, a total compensation of \$355 plus applicable travel compensation will be provided as study events are completed. Participants will receive study compensation via check.

5.3 Informed Consent Procedures

The study team has obtained Waiver of Documentation of Consent from the IRB for participant fasting prior to the study screening visit. Participants will be asked for verbal confirmation of their willingness to fast overnight prior to the study screening visit.

Screening visits (up to 60 minutes duration) will occur in the morning at the Endocrinology Clinic space at the Harry S Truman VA Hospital. Informed written consent will be obtained by [name] in a private and non-rush environment. [name] is trained and compliant with IRB and HIPAA education requirements. Sufficient time will be provided for the subject to read and review the documents. [name] will answer any questions that the potential participants may have and will assess understanding of the study consent by asking subjects simple questions about the study purpose and the procedures involved. As described in the informed consent, [name] will reiterate to the subjects that: 1) participation is completely voluntary, 2) decision to participate or not will not influence their relationship with the physician or any member of the research team; and 3) participant may withdraw from the study at any time for any reason. For all subjects, a HIPAA Authorization form will also be obtained as approved by the VA. One copy of the executed consent and HIPAA Authorization form will be given to the subject and one copy will be stored in a secured file cabinet. [name] will perform a pertinent medical history on all subjects.

5.4 Inclusion/Exclusion Criteria

Inclusion:

- 1) 45-74 years of age at the time of enrollment
- 2) Diagnosis of T2D by a health care provider, confirmed by chart review
- 3) HbA1c <9% and fasting blood glucose <200 mg/dL at screening visit
- 4) Body mass index (BMI) 25–45 kg/m²
- 5) Women should be postmenopausal (absence of menses for at least 1 year)
- 6) Sedentary subjects (<2 days/week of vigorous exercise)
- 7) Willingness to follow up instructions provided by study team

Exclusion:

- 1) Evidence of cardiac arrhythmias, unstable angina (or other cardiac event), heart failure or stroke in the last 12 months
- 2) Evidence of chronic kidney disease stage IV or V (GFR <30 mL/min)
- 3) Evidence of uncontrolled hypertension, systolic blood pressure > 180 mmHg and/or diastolic blood pressure > 110 mmHg on more than 2 occasions in the past 12 months or at screening visit
- 4) Diagnosis of chronic liver disease
- 5) Uncontrolled thyroid dysfunction (abnormal TSH within 3 months of study enrollment)
- 6) Active cancer
- 7) Current use of hormone replacement therapy
- 8) Excessive alcohol consumption (>14 drinks/week for men, >7 drinks/week for women)
- 9) Current pregnancy or intent to become pregnant during the course of the study
- 10) Inability to swallow capsules
- 11) Known allergies to any of the compounds in the supplement: glucosamine extract, fucoidan extract, olive extract, artichoke extract, red and white grapes extract, melon concentrate, hyaluronic acid

	Screening Visit	AMBP Fitting (Day -7 to -2)	Pre- Assessment (Day 0)	Safety Blood Draw (Days 7-14)	Dosing Window (Days 1-56)	AMBP Fitting (Day 49-54)	Post- Assessment (Day 56)
Informed consent form signing	X						
Medical history	X						
Concomitant medication assessment	X		X		X	X	X
Height assessment	X		X				X
Weight assessment	X		X				X
Waist circumference assessment	X		X				X
Vitals signs (blood pressure, heart rate and respiratory rate, temperature)	X		X				X
12-lead ECG	X						
Fasted bloodwork: HbA1c, FLP, CMP, TSH, H&H	X						
Bloodwork: PT, PTT, H&H	X			X			X
3- Day food diary		X				X	
24-hour Ambulatory Blood Pressure Monitoring (AMBP)		X				X	
24-hour AMBP activity log		X				X	
AM T2D medication hold			X				X
AM Tobacco hold	X		X				X
24-hour exercise hold	X		X				X
Overnight fasting	X		X				X
Fasted blood draw			X				X
Glycocheck		X	X				X
Pulse Wave Velocity			X				X
Brachial FMD			X				X
Femoral FMD			X				X
Insulin and glucose infusion with leg blood flow, sphygmomanometry, and beat- to-beat via finometer			X				X
Contrast enhanced ultrasound			X				X
DEXA			X				X
Supplement/placebo dispensing			X				
Daily Supplement/Placebo dosing					X		
Weekly phone check-in					X		

Table 1. Schedule of study activities. Note that after screening visit, once eligibility has been confirmed subject will be randomized.

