Pulse wave velocity: A special non-invasive device will be used to assess blood pressure and flow. A blood pressure cuff will be wrapped around the upper arm and upper leg of the participant. The cuffs will periodically inflate to squeeze tightly for less than 60 seconds. A pressure sensor, the size of a pencil will be placed over the skin of the neck region to obtain the pressure wave form in the neck vessel (i.e., carotid artery). This procedure takes about 15 minutes. Risks: The blood pressure cuff will squeeze the arm and leg tightly; however, any discomfort will be alleviated as soon as the pressure in the cuff is released. This procedure is not standard of care.

Brachial and femoral artery FMD: Arterial measurements will be performed by imaging the brachial or femoral artery longitudinally using high-resolution duplex ultrasonography. Arterial vasodilatory responses to hyperemia (i.e., FMD) will be examined by inflating a forearm or leg cuff up to 250 mmHg for five minutes. Before, during and after rapid release of the cuff, brachial artery blood flow velocity and diameter will be continuously measured. When assessing FMD, the blood pressure cuff will squeeze the arm or leg tightly; however, any discomfort will be alleviated as soon as the pressure in the cuff is released. This procedure is not standard of care.

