ultrasound imaging of the leg skeletal muscle during the administration of one vial (1.3 mL) of an ultrasound contrast agent diluted in 30 mL of 0.9% saline that will be given using a handheld syringe pump through the IV at a rate of 2 mL/min. This agent, called Definity, is composed of tiny microbubbles smaller than the size of a red blood cell. These bubbles stay inside the blood vessels and go where the red blood cells go. This contrast agent allows us to evaluate microvascular blood flow. Definity has been FDA approved for use in humans during ultrasound of the heart cavity and has been shown to be safe. The total volume of blood drawn per insulin infusion is approximately 52mL. The potential risks during this procedure include mild nausea or light-headedness, and mild to moderately high or low blood glucose levels. However, blood glucose will be continually monitored during the infusion of insulin and dextrose will be available if needed to counteract hypoglycemia. Also, drinks and snacks will be available for the subjects at the completion of testing should they have low blood sugar or feel nauseous. Subjects are monitored for a minimum of one hour post insulin infusion. This procedure is routinely performed by Drs. [name] and [name]. [name], board-certified endocrinologist, will be available during the procedures. This procedure is not standard of care.

Skeletal muscle perfusion assessment using Perflutren (Definity): A potential side effect from the Perflutren ultrasound contrast agents is temporary back pain, joint pain, headache, shortness of breath, or flushing. These symptoms occur in about one in 200 subjects and are mild in intensity in 90% of those who experience this reaction. If this happens infusion of the agent will be stopped. The back and joint pain will go away in a few minutes. A serious allergic reaction to ultrasound contrast agents is unlikely (1 in 10,000), but possible. Symptoms of an allergic reaction include: Rash, itching, swelling, severe dizziness, chest pain and trouble breathing. We are using this contrast agent to measure microvascular perfusion in skeletal muscle using a dose approved by the FDA. This procedure is not standard of care.

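### Section 5.4 excludes known allergy to the supplement but not known hypersensitivity to the ultrasound contrast agent that every subject is scheduled to receive twice

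*Combined protocol and SAP*

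**What the plan says.** Section 5.4 lists 7 inclusion and 11 exclusion criteria. Exclusion 11 reads "Known allergies to any of the compounds in the supplement" and goes on to name the ingredients. Section 5.5 repeats it under the supplement heading, directly after stating that supplementation carries no known risks.

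The row "Contrast enhanced ultrasound" in Table 1 is marked at the pre-assessment (Day 0) and the post-assessment (Day 56), with no subset of subjects. Section 5.5 describes the procedure as "ultrasound imaging of the leg skeletal muscle during the administration of one vial (1.3 mL) of an ultrasound contrast agent", diluted and given intravenously. On its risks, the perflutren paragraph of section 5.5 says "A serious allergic reaction to ultrasound contrast agents is unlikely (1 in 10,000), but possible" and lists the symptoms of such a reaction.

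Section 7.0, under protection against risks, puts adherence to the eligibility criteria first among the means of limiting risk.

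**The concern.** The protocol screens for allergy to a product it describes as having no known risks. It does not screen for allergy to an agent that it says can cause a serious allergic reaction. Someone with a documented past reaction to the contrast agent would satisfy section 5.4 and be scheduled for two administrations.

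What is at stake is the safety of an individual subject, not the statistical analysis. Because section 7.0 relies on the eligibility list to limit risk, a hazard missing from that list is not controlled by that route.

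**Working it through.** The point concerns what the eligibility list contains, so there is no plan figure to reproduce. The first part compares the texts; the second gives a rough size.

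**Comparison**

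| Item | Supplement | Ultrasound contrast agent |
|---|---|---|
| Who receives it | Half the subjects (12 of 24 in Aim 1) | All subjects, at two visits (Table 1) |
| Allergic risk stated in 5.5 | No known risks | Serious reaction, 1 in 10,000 |
| Exclusion for known allergy | Yes (exclusion 11, repeated in 5.5) | None |
| Stated handling in 5.5 | Not enrolled if allergic | Infusion stopped if symptoms occur |

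The statement about stopping the infusion follows the list of milder side effects. No screening step precedes it. Other places where a contrast rule might sit:

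- Section 5.3: a medical history is taken on all subjects, with no rule attached to contrast allergy.
- Section 5.5, screening: the co-PIs review eligibility, with no such rule.
- Section 6.0: the safety officer reviews the eligibility criteria, with no such rule.
- Section 5.5, DEXA: there is an exclusion for prior radiation exposure, which is unrelated.

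**Size**

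Inputs: 24 Aim 1 subjects (section 5.6), two contrast visits (Table 1), and a serious-reaction rate of 1 in 10,000 (section 5.5).

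1. Administrations in Aim 1: 24 × 2 = 48.
2. Background risk in unselected people. Taking the rate per administration (assumption), the expected number is 48 × 0.0001 = 0.0048, and P(at least one) = 1 − 0.9999^48 = 0.48%. Taking it per subject, 1 − 0.9999^24 = 0.24%.
3. Chance that the 24 include someone with a past serious reaction. The documents do not say how many candidates have met the agent before. If all had one earlier exposure (assumption), P = 1 − 0.9999^24 = 0.24%. If one in ten had (assumption), the expected number is 24 × 0.10 × 0.0001 = 0.00024, or about 0.024%.
4. Candidates lost. Section 5.2 expects about 200 people to be consented across both aims. With one earlier exposure each, 200 × 0.0001 = 0.02 people would be turned away.

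Step 2 is the risk in people without a known history. An exclusion would not remove it, and the documents give no reaction rate for people with a known history. Steps 3 and 4 do not count people with a known allergy to a component of the agent who have never received the agent itself. The documents do not allow that number to be estimated.

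The rate of about 1 in 200 in section 5.5 refers to side effects such as back pain and headache. The protocol does not call these allergic, so that rate is not used to size the gap.

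**The case against.** The strongest reply is that clinical judgement already covers this. A physician takes a history, the co-PIs review eligibility, the safety officer reviews the criteria, section 5.7 allows withdrawal for a safety concern, and the infusion is stopped if symptoms occur. Consent pages were also removed from the text under review, so any allergy question there cannot be seen. Part of this stands: the documents do not show that such a person would in fact be infused. They show only that no written criterion prevents it, and none of the layers visible in the text states a contrast rule. The low probability also stands, and it limits the weight of the point.

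A reader might infer two stronger claims that the documents do not support.

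- **That section 5.4 ignores procedure hazards in general.** It does not. The cardiac and blood-pressure exclusions bear on the infusion and cuff procedures, and section 5.5 adds the radiation exclusion for DEXA.
- **That leg arterial disease is a comparable safety and validity failure.** The vascular-event exclusion is "Evidence of cardiac arrhythmias, unstable angina (or other cardiac event), heart failure or stroke in the last 12 months", and femoral flow-mediated dilation (FMD) involves "inflating a forearm or leg cuff up to 250 mmHg for five minutes", so leg disease is indeed not addressed. But section 5.5 lists only passing discomfort as a cuff risk, and the documents give no prevalence of leg disease and no hazard figure. PBR, on which Aim 1 is powered, comes from a sublingual measurement. Brachial FMD is also taken, and section 5.6 does not name the leg measures as secondary outcomes. Excluding leg disease from a vascular study in type 2 diabetes is a debatable trade-off.

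**Conclusion.** The point holds for the contrast agent. Section 5.4 and the perflutren paragraph of section 5.5 are out of step, and a subject with a known past reaction is eligible as written. This is a low-probability safety gap: at most about 0.24% for Aim 1 on the assumption of one earlier exposure per subject and the protocol's own rate, leaving aside known component allergies. It does not affect the primary analysis. The change is worth making because the protocol names the hazard, every subject is scheduled for it twice, and a history question can detect it.

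For leg arterial disease, only a secondary note is justified: the plan is silent on how such subjects are handled although femoral FMD and leg blood flow are measured before and after treatment. No size can be put on it from the documents.

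**What to change.** Reconcile section 5.4 with the contrast-agent risk text in section 5.5 by extending exclusion 11 to known hypersensitivity to the ultrasound contrast agent and its components. The investigators should set the exact wording. Apply it through the medical history already taken at screening, and repeat it in the perflutren paragraph, as section 5.5 already does for the supplement.

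The cost is one line of protocol text and one screening question, with no new test. Very few candidates would be lost from a pool that section 5.2 puts at 1,476 endocrinology patients with type 2 diabetes and 9,400 in primary care (the two groups may overlap).

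Separately, add a sentence saying how subjects with known leg arterial disease are handled for femoral FMD and leg blood flow. The choice of rule belongs to the investigators.
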